3. STUDY DESIGN

This study is funded through a R61/R33 phased award from the NIH HEAL Initiative. The R61 Phase 1 Specific Aims are as follows. In preparation for a larger scale, pragmatic 2x2 factorial trial, we aim to:

1. Refine and manualize IGMV in English and Spanish with stakeholder input and informed by relevant theory.
2. Test randomization procedures, contamination, and intervention fidelity in 40 patients with chronic pain.
3. Determine if there is preliminary evidence for our hypothesized mechanisms of action on improved pain management. We will collect and analyze data on pain outcomes, social isolation, and intersectional stigma.

Here we focus on procedures for specific aim 2, a pilot trial designed to assess the feasibility of key study design procedures for a larger trial.

- We will use a 2x2 factorial randomized clinical trial design.
- The primary feasibility outcome for the study is randomization of participants. The secondary feasibility outcomes include participant retention, intervention fidelity, and intervention adherence. We will also assess degree of bias and contamination between study groups.
- We will also assess quality and variability of data on patient-reported pain-related outcomes. These include pain interference, social isolation, average weekly pain severity, social support for chronic pain, health-related quality of life, depressive symptoms, anxiety, sleep disturbance, internalized stigma of chronic pain, and pain self-efficacy.
- Study population will consist of adult patients 18 years of age and older who have painful diabetic neuropathy and have been seen for their diabetes at SFGH clinics within the past year. Forty participants will be enrolled and randomized to four arms (10 in each group): (a) usual care, waitlist comparison, (b) usual care combined with group acupuncture once weekly, (c) usual care with integrative group medical visits, (d) usual care with group

acupuncture and integrative group medical visits. Participants, practitioners, and assessors will not be blinded. The statistician will be blinded to participant assignment.

- All study procedures will take place at the UCSF Osher Center for Integrative Health and at the SFHN Castro Mission Health Center. Recruitment efforts will be through the Tom Waddell Urban Health Clinic, Castro Mission Health Center, and the Family Health Center.

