4.3 Study Enrollment Procedures

Screening and Consent

- We will use electronic health records to pre-screen patients who meet key eligibility criteria: age, chronic pain diagnosis, primary language, and empaneled with primary care provider at a study site.
- We will present a list of pre-screened patients to primary care providers to confirm eligibility and approval for enrollment.
- Clinical research coordinators (CRCs) will contact eligible patients by telephone to invite them to participate in a study to improve pain management in primary care.
- During the telephone call, CRCs will ask eligible patients about their preferred method of contact (i.e., phone, text message, and/or email) to schedule an orientation session and to receive reminders about the orientation session. The study team will also ask eligible patients for permission to send text message reminders and whether the study team can leave voicemail messages.
- We will also host orientations with eligible patients as an additional opportunity for them to learn about the study.
- CRCs will also be available to discuss the study in person with patients who are scheduled for upcoming appointments.
- CRCs will obtain informed consent from eligible patients who are interested in participating.

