4.4 Data Collection and Randomization

- Following the consent process, CRCs will conduct a baseline assessment with study participants. Baseline data collection will include sociodemographic, pain symptoms, mood, daily activities and open-ended questions regarding social isolation, stigma, and experiences with pain care.
- After the baseline assessment, participants will be randomized to one of four groups (described in more detail below). To maintain participant flow and adequate staggering of acupuncture and IGMV, we will use computer-generated, randomly permuted blocks of 4 and 8, stratified by language. The database manager who will not be involved with enrollment will program the random allocation sequence; no other study staff will have access to generating the randomization sequence. The CRC will access the allocation

sequence using a programmed database that cannot be altered once the randomized condition is revealed.

- Participants randomized to study interventions will participate in weekly sessions for twelve weeks and those randomized to Integrative Group Medical Visits have the option to participate in focus groups immediately following the final weekly session.
- Three months after baseline, participants will complete validated surveys about pain symptoms, social isolation, quality of life, and other pain-related symptoms and open-ended questions about pain management.
- Three months after baseline, participants will also complete semi-structured interviews on participants' experiences living with chronic pain, and their perspectives on non-pharmacologic pain treatment, including participation in the study.
- Interviews will focus on participants' experiences treating chronic pain, perspectives on non-pharmacologic treatment, and experiences referring patients to the Integrative Pain Management Program (i.e., the larger RCT component of this study). These interviews will last 45-60 minutes and take place in-person or virtually at a private location of the participant's preference (e.g., the participant's office, UCSF Osher Center for Integrative Health offices, or via Zoom). At the time of the interview, participants will complete a brief demographic form (including gender, racial and ethnic identity, years of clinical experience, and chronic pain treatment experience). No EHR data of any kind will be collected for providers participating in the provider interview subsample.

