9.2 Statistical Analysis Plan

Descriptive analyses

Baseline characteristics of participants, including sociodemographics and health condition variables, will be summarized to determine sample generalizability, and compared to assess group equivalency. We will look at summary statistics for data cleaning (e.g., means, ranges)

and then consider distributions by randomized arm as a check of balanced distribution across groups.

Analysis of Feasibility. Feasibility outcomes will be analyzed by computing percentages, with 95% confidence intervals, of rates of retention and enrollment. We will also conduct a thematic analysis of qualitative responses on participants' experiences with the study and acceptability of group acupuncture.

Assessment of implementation, defined as quality and consistency of the intervention delivery across staff, will be focused on evaluating core components and content of IGMV and parameters in STRICTA guidelines for group acupuncture. IGMV facilitators will complete a short survey after each session documenting content and time spent on each component. Acupuncturists will complete charting for each treatment provided.

Analysis of Patient-Reported Outcome Measures. This study is powered to assess exploratory effects and pilot feasibility, not for confirmatory analysis. Nonetheless, we will analyze clinical outcomes in a manner similar to that planned for the main study to make a preliminary assessment of the strength of the effects; to identify any unexpected issues with missing data, skewed distributions, or outliers; and to refine the statistical analysis plan. Relative (mean \pm SD) measures of effect sizes will be calculated as change from baseline to post-intervention for all outcome variables. Planned analyses include: within group changes from baseline to Week 12, group acupuncture vs. no acupuncture, and IGMV vs. no IGMV.

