Treatment effects will be estimated using a repeated measures ANCOVA approach. The framework is similar to a linear mixed models but it includes the baseline of the outcome as a covariate (and omits the baseline from the outcome vector), and the models will include indicators for assignment to acupuncture, IGMV, a categorical variable for time, and interactions between treatment indicators and time, as well as random intercepts for person nested within group to account for within-group and within-patient correlation of the repeated measures. Models with a three-way interaction between the two treatment indicators and time will be evaluated as a first step to assess for synergy between IGMV and group acupuncture. We will also calculate an interaction ratio to assess clinically meaningful antagonism or synergy between the two interventions, specified as interaction ratios of ≤ 0.80 or ≥ 1.25 .⁴⁶ If there is evidence of interaction, we will assess marginal effects of each intervention. If no evidence of synergy is identified, we will proceed with models that omit the three-way interaction term, to instead focus on main effects of each treatment type. This approach will optimally weight data for patients with different numbers of responses, and will provide valid estimates in the presence of missing data under relatively mild assumptions about how the missing data arise.⁴⁷ We will conduct intent-to-treat, per protocol, and complier average causal effects analyses; and exploratory as treated analysis (receipt of any group integrative health intervention and dose-response based on number of sessions attended). Outcomes will be normalized as needed to meet model assumptions; for outcomes which do not meet distributional assumptions of normality, other generalized linear mixed models or non-parametric approaches such as Kruskal-Wallis tests will be used. Secondary outcomes will also be analyzed using this approach.

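### Minor: randomization is stratified by language but the outcome model omits it, so the limits are slightly too wide if language predicts outcome beyond baseline

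*Combined protocol and SAP*

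**What the plan says.** Section 4.4 allocates participants by "randomly permuted blocks of 4 and 8, stratified by language". Section 4.1 limits the strata to English and Spanish. Section 4.3 shows that language is known before enrollment, because the health-record pre-screen covers "age, chronic pain diagnosis, primary language, and empaneled with primary care provider at a study site".

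Section 9.2 describes a repeated-measures ANCOVA with the baseline of the outcome as covariate. It states that "the models will include indicators for assignment to acupuncture, IGMV, a categorical variable for time", then adds treatment-by-time interactions and "random intercepts for person nested within group". Language is not in this list, and no other section adds it to the outcome model. Section 6.2 lists descriptive covariates but does not say that any of them is adjusted for.

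For outcomes that still fail normality after transformation, Section 9.2 says that "other generalized linear mixed models or non-parametric approaches such as Kruskal-Wallis tests will be used".

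Section 9.1 sets the pilot effect estimate, with a one-sided 80% limit, against a target of 0.25 SD. It goes on to tie the decision to proceed to whether the estimate is above zero and the procedures prove feasible and acceptable.

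**The concern.** Stratified blocks make the arms similar in language mix. Differences between English and Spanish speakers then contribute little to the real sampling error of the acupuncture and IGMV contrasts. A model without language still counts those differences as residual noise, so its standard errors exceed the true spread of the estimate to the extent that language predicts outcome after baseline adjustment. The usual principle is to analyze by the factors that the randomization used.

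The stakes are limited to the interval that Section 9.1 compares with 0.25 and to the template for the main study. Section 9.2 says that clinical outcomes will be analyzed much as in that study, partly to refine its analysis plan, so a mismatch left here is likely to be carried forward.

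There is a smaller side issue. Kruskal-Wallis yields neither a covariate-adjusted effect nor a confidence limit, so an outcome analyzed only that way would have no adjusted estimate to compare with 0.25.

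**Working it through.** **The plan's own figures.** 9% of 360 = 0.09 × 360 = 32.4, stated as at least 32. Allowing for 20% attrition, 32 / 0.80 = 40. Both reproduce.

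**Inputs from the documents.** 40 randomized to four equal arms (Section 3); blocks of 4 and 8 within language (Section 4.4); 20% attrition, hence 32 completers, and a one-sided 80% limit (Section 9.1); one follow-up at three months (Section 1.2).

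**Assumptions, because the documents are silent.** Language split 25/15; completers a random 32 of 40; correlation of baseline with follow-up 0.5; SD 1 within language; no clustering; true effect zero.

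**Expected size by hand.** Residual variance after baseline is 1 − 0.5² = 0.75. A language gap *d* remaining after baseline adjustment adds *p*(1 − *p*)*d*², with *p* = 15/40 = 0.375 and *p*(1 − *p*) = 0.234. Leaving language out inflates the standard error by about 1/√(1 − R²), where R² is language's share of that residual variance.

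- Gap of 0.5 SD at baseline and follow-up: about 0.5 − 0.5 × 0.5 = 0.25 remains. Added variance 0.234 × 0.0625 = 0.0146; R² = 0.0146/0.7646 = 0.019; inflation about 1.0%.
- Gap of 0.5 SD at follow-up only: added variance 0.234 × 0.25 = 0.0586; R² = 0.0586/0.8086 = 0.072; inflation about 3.8%.

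From each, subtract about 0.5%, the price of the extra term when completers are not perfectly balanced.

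**Simulation.** Blocks of 4 and 8 within language, 32 random completers, ANCOVA with acupuncture, IGMV and baseline, without and with language:

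| Language gap | SE without | SE with | Change from omitting language | Sign of estimate differs |
|---|---|---|---|---|
| None | 0.3111 | 0.3126 | 0.5% narrower | 2.8% |
| 0.5 SD at both times | 0.3140 | 0.3125 | 0.5% wider | 3.2% |
| 0.5 SD at follow-up only | 0.3247 | 0.3134 | 3.6% wider | 5.4% |

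A repeat with 12,000 runs per setting gave 0.3111 v 0.3127, 0.3146 v 0.3136 (0.3% wider) and 0.3237 v 0.3127 (3.5% wider), with sign changes of 2.9%, 3.4% and 5.2%.

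**Wider range.** With 30% or 50% Spanish speakers and an assumed partial R² for language, the one-sided 80% half-width without language is about 0.5% wider at R² = 0.02, 2% at 0.05, 5% at 0.10 and 12% at 0.20. Coverage of the nominal 80% limit without language rises from about 0.79-0.80 at R² = 0 to about 0.82 at R² = 0.20. With language it stays at about 0.79-0.81.

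**Section 9.1's statement about a zero estimate.** With language in the model, 32 completers leave 27 degrees of freedom, for which the 80% quantile of *t* is 0.855. With no gap, the upper limit at a zero estimate is 0.855 × 0.3126 = 0.267. With the follow-up-only gap it is 0.855 × 0.3134 = 0.268. Both exceed 0.25. In the wider range the half-width with language is still 0.254 at R² = 0.10. It falls below 0.25, to 0.240, only at R² = 0.20.

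**The case against.** The strongest reply is that this hardly matters. The error is conservative, the pilot is not confirmatory, its primary outcome is the percentage of confirmed eligible patients randomized, and the rule to proceed turns on the sign of the estimate, which a wide standard error cannot change. With a 0.5 SD gap already present at baseline, the gain from adding language is no larger than the cost when language is irrelevant. All of this stands, and it is why the point is minor.

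Several stronger readings are tempting but not supported:

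- *The limits are too wide as the plan stands.* This holds only if language is prognostic beyond baseline. The documents give no figure on that.
- *The decision to proceed is compromised.* Adding language changes the sign in about 3-5% of runs, but about 3% occurs with no gap at all. Most of this is the ordinary jitter of estimates near zero.
- *Adding language would make Section 9.1's statement about a zero estimate true.* At the gaps assumed here it would not.
- *Groups run by language, so the effect is larger or the group intercept already absorbs it.* Section 3 plans to "Refine and manualize IGMV in English and Spanish with stakeholder input and informed by relevant theory", but no section says that sessions are separated by language, and participants in the usual-care arm attend no group.
- *The fallback leaves outcomes without an effect estimate.* Section 9.2 tries transformation first and also offers generalized linear mixed models, which can keep the planned terms. It also says that "measures of effect sizes will be calculated as change from baseline to post-intervention for all outcome variables", and it plans the contrasts "group acupuncture vs. no acupuncture, and IGMV vs. no IGMV". What stands is narrower: no interval is stated for those change-based effect sizes, and Kruskal-Wallis supplies none.

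**Conclusion.** The mismatch between randomization and analysis is certain from the text; its consequence is conditional and small. If language predicts outcome beyond baseline, reported standard errors and the one-sided 80% limit are slightly too wide. If it does not, they are correct. Under the stated assumptions the excess is about 0.3-0.5% for a 0.5 SD gap carried by baseline and about 3.5% for a gap that appears only at follow-up. Larger values need a stronger language effect than 0.5 SD, and nothing in the documents indicates one. Treatment estimates are not biased, and the feasibility outcomes do not use this model. This is a minor correction, worth making because it is nearly free and the model is a template for the main study.

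**What to change.** In Section 9.2, add to the list of model terms: *language (English/Spanish), the randomization stratification factor, as a fixed effect in the model for every patient-reported outcome*. Keep the planned group intercept.

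The cost is one phrase and one degree of freedom, with about 0.5% on the standard error if language turns out to be irrelevant. No new data are needed, because language is recorded at pre-screening and used to stratify.

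At most, add one sentence after the non-parametric fallback: any outcome compared with 0.25 under Section 9.1 keeps an estimate and limit from the planned mixed model, with Kruskal-Wallis as supplementary. A bootstrap limit that resamples individuals within arm is not a good substitute, because it drops the group intercept. In a check at an assumed within-group correlation of 0.05, its standard error was 0.295 against a true spread of 0.338.

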- The full enrollment period for the study will take place in waves over 2-3 months depending on the rate of recruitment and the success of enrollment. Once the initial 6 participants are enrolled and consented, they will be randomized to the three treatment arms (randomization procedures are included in Section 4.3). Data collection and treatment will begin for the initial 6 participants while recruitment and enrollment continue on a rolling basis for the remaining study participants. The estimated duration of study involvement for each participant is approximately six months, which includes a 12-week intervention and a 3-month follow up interview post-intervention.
- Description of intervention and administration: All study participants will receive usual care. In addition, some participants will be randomized to receive group acupuncture for a period of 12 weeks, once per week. Some participants will be randomized to receive integrative group medical visits for a period of 12 weeks, once per week.

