5. STUDY INTERVENTIONS

Study interventions are based on stakeholder input and patient preference, and the extent that they: (1) reflect real world practices that are viable options in primary care safety net settings, and (2) could be standardized to enhance replicability in future studies or in clinical practice. Study participants will be randomized to one of four experimental conditions:

- i. Usual care. Participants will receive care as usual provided through their primary care providers. Usual care includes medical diagnostic evaluation, analgesic drug therapies, recommendations for physical activity, and sometimes referral to specialist physicians or physical therapy. Usual care was chosen as a comparison arm for this study because it is practical and clinically relevant. One challenge with using a usual care arm in a clinical trial is the potential variability in the care provided in clinical practices.²⁰ EHR data will be extracted and reviewed to accurately describe usual care for study participants.

ii. **Integrative Group Medical Visits for Pain.** IGMV will consist of a 12-week program that provides education on the biopsychosocial model of pain and multimodal treatments; physical movement; mindfulness training; and peer support. Non-pharmacologic approaches were chosen based on guidelines on chronic pain management; feedback of experts, staff, and patients,²¹ and feasibility with the greatest potential to benefit participants. Participants will receive a binder with educational materials. Weekly IGMV sessions will be two hours in a group meeting space at the clinics. Sessions will start with a “check-in” where participants can share their emotions, thoughts, hopes, and fears related to their health and provide updates since the last session. Group sessions will be led by a primary care provider and a health educator and will include psychosocial support, tools for pain self-management, and psychoeducation for pain management.^{22,23} Following the group “check-in,” an invited guest (example: pharmacist, mindfulness expert) will provide information on

educational topics, including neurobiology of pain, medication safety, and connections between mood and pain (see table 1 for sample content based on prior IGMV), as well as participatory activities such as therapeutic movement or mindfulness practice.

Table 1. Sample IGMV Content

Week	Content	Facilitator(s)*

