1	Orientation – goals, neurobiology of pain, pain stories, treatments & self-care	Health Educator & Program Coordinator (group facilitators)
3	Mindfulness, physical movement	Certified yoga instructor
4	Thoughts & pain, medication education	Clinical Pharmacist
5	Stress & pain, meditation/mindfulness	Mindfulness instructor
6	Emotions & pain	Clinical psychologist
7	Self-massage	Certified massage therapist
8	Pacing, physical movement	Certified yoga instructor
9	Nutrition, meditation/mindfulness	Nutritionist, mindfulness instructor
10	Sleep & pain	Clinical Pharmacist
11	Relationships & pain	Clinical psychologist, educator
12	Moving forward, graduation	Program Coordinator

* Primary care provider present at all sessions

iii. **Group Acupuncture.** Acupuncture was selected based on: (1) strength of supporting evidence and inclusion in clinical guidelines,^{8,9,24-26} (2) high acceptability and feasibility in our target population as demonstrated in our preliminary studies, and (3) substantial access barriers for socioeconomically disadvantaged patients due to lack of insurance coverage. Participants randomized to acupuncture will receive 12 weeks of acupuncture treatments delivered in a group setting, dosing similar to prior research.^{15,16} Acupuncture point selection and other treatment details will follow responsive manualization, a protocol developed for the largest RCT of group acupuncture to date.^{15,27} A licensed acupuncturist experienced with administering group acupuncture treatments will determine each participant’s traditional Chinese medicine diagnosis and administer 8-10 acupuncture needles on distal points of participant’s body (below the knees, from the elbows to the hands, and on the head). Duration of assessment, needle placement and retention will be 30-45 minutes. Details of acupuncture treatments (e.g., frequency and duration, TCM diagnosis, number of needles and points used) will be documented in standard EHR charting used by the Osher Center for Integrative Health.²⁸

iv. **Both group acupuncture and IGMV.** Along with usual care, participants will be offered weekly group acupuncture treatments and integrative group medical visits as described above.

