9. STATISTICAL CONSIDERATIONS

9.1 Sample Size Rationale

The study will enroll 40 participants. As a small pilot study designed to pilot the refined intervention, we did not conduct a formal power calculation but instead used a confidence interval approach to determine sample size, based on current recommendations for small samples. Findings from the pilot study are intended to help plan for a future trial by estimating key parameters. However, small trials often overestimate treatment effects and the convention of basing power calculations on pilot trials has received considerable scrutiny (Kraemer, 2006). Our approach will be to determine whether the effect size from the pilot is clinically meaningful (i.e., within an 80% confidence interval of a pre-determined effect size) and justifies proceeding with future research. To determine this, Cocks and Torgenson (2013) recommend that a pilot sample size should be at least 9% of the sample size of the planned main study.

Based on data of minimally important differences for PROMIS pain measures, our main study would aim to detect a standardized effect size of 0.25. Using our pilot data to estimate within group correlation and a sample size calculator designed for individually randomized group trials, we estimated a sample size of 360. Using Cocks and Torgenson's method, the corresponding pilot sample size should be at least 32. Using an estimated attrition of 20%, we aim to enroll 40 participants. With 20 participants randomized to each of the study interventions, we will have sufficient power to determine if the effect size estimated from the pilot is within the range of clinical significance using a one-sided 80% confidence interval. If the estimated effect is zero or less, the upper 80% CI will not contain our target effect size of 0.25, and we would not proceed with a main study. If the estimated effect size from the pilot is larger than zero, and the study procedures are feasible and acceptable, then we would have sufficient preliminary data to proceed with the main study.

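### The outcome model gives each person one undefined group, so it cannot represent acupuncture-group and IGMV-group clustering separately for the 10 of 40 participants who attend both

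*Combined protocol and SAP*

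**What the plan says.** Section 9.2 (Statistical Analysis Plan) estimates treatment effects on the patient-reported outcomes with fixed indicators for acupuncture and IGMV, and with "random intercepts for person nested within group to account for within-group and within-patient correlation of the repeated measures". No section defines group in this sense.

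Section 3 sets the allocation: "Forty participants will be enrolled and randomized to four arms (10 in each group"). Both interventions are delivered in groups. The précis describes acupuncture given in a shared room with several recliners, and Section 5 says "Weekly IGMV sessions will be two hours in a group meeting space at the clinics". For the fourth condition, Section 5 says "participants will be offered weekly group acupuncture treatments and integrative group medical visits as described above".

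The plan treats clustering as real. Section 9.1 sizes the main study "Using our pilot data to estimate within group correlation and a sample size calculator designed for individually randomized group trials". Section 9.2 says the clinical outcomes will be analysed "in a manner similar to that planned for the main study", with refinement of the analysis plan as one aim.

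**The concern.** A person nested within a group belongs to exactly one group. That fits the two single-intervention arms. It does not fit the combined arm, whose members sit in an acupuncture group and an IGMV group each week, or the waitlist arm, whose members sit in neither. The plan does not say which group a combined-arm participant is nested in, how waitlist participants are coded, or whether the combined arm shares sessions with the single-intervention arms.

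Two things are at stake. The first is the reported precision of the two intervention effects, including the one-sided 80% limit of Section 9.1 if it is taken from this model. The second is information for the main trial. Section 9.1 wants the pilot to estimate key planning parameters and relies on a within-group correlation. A single group term cannot yield one correlation for acupuncture groups and another for IGMV groups.

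**Working it through.** **The plan's own figures.** Section 9.1: 0.09 × 360 = 32.4, stated as 32; 32 / 0.80 = 40 enrolled. Then 40 / 4 = 10 per arm, 10 + 10 = 20 per intervention margin, and 10 / 20 = half of each margin is the combined arm. After 20% attrition, 32 / 4 = 8 completers per arm.

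**Assumptions (not in the documents).** 2 or 4 equal groups per format, shared between the single and combined arms; ICC 0.01, 0.05 or 0.10 within a format; waitlist participants as singletons, except under the wave reading, where they share the wave; main-effects model with intercept, acupuncture and IGMV.

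**Method.**
- True covariance: V = σ²_A Z_A Z_A′ + σ²_I Z_I Z_I′ + σ²_e I, with ICC = σ²_g / (σ²_g + σ²_e) for each format.
- Fitted covariance: W = τ² Z Z′ + σ² I, with one identifier per person; τ² and σ² minimise the expected REML criterion under V.
- With M = (X′W⁻¹X)⁻¹, the reported variance is M and the actual variance is M X′W⁻¹ V W⁻¹X M.
- Ratio = reported SE / actual SE. Coverage of a nominal one-sided 80% limit = Φ(0.842 × ratio).

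Example: ICC 0.10, two groups per format, combined arm coded by its IGMV group. For acupuncture the reported SE is 0.352 and the actual SE 0.405, so the ratio is 0.869; 0.842 × 0.869 = 0.732 and Φ(0.732) = 0.768.

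**Results, equal ICC in both formats**

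| Meaning of group | Effect | Groups or waves | Ratio at ICC 0.01, 0.05, 0.10 | Coverage |
|---|---|---|---|---|
| Combined arm carries one format's ID | other format | 4 | 0.993, 0.967, 0.935 | 0.798, 0.792, 0.784 |
| | other format | 2 | 0.985, 0.931, 0.869 | 0.797, 0.783, 0.768 |
| | format whose ID is used | 2-4 | 1.003 to 1.033 | 0.801 to 0.808 |
| ID per group combination, cohorts stay together | both | 4 | 0.999, 0.995, 0.989 | 0.800, 0.799, 0.797 |
| | both | 2 | 0.996, 0.979, 0.956 | 0.799, 0.795, 0.789 |
| Enrolment wave | both | 4 | 0.992, 0.963, 0.927 | 0.798, 0.791, 0.782 |
| | both | 2 | 0.982, 0.916, 0.845 | 0.796, 0.780, 0.762 |

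The combination rows assume that combined-arm members of one acupuncture group also share one IGMV group. If memberships cross, the same formula at ICC 0.10 gives 0.969 (4 groups) and 0.927 (2 groups), with coverage 0.793 and 0.782.

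**Clustering in IGMV only.** If the combined arm carries the IGMV identifier, the ratios are 1.001 to 1.027 for acupuncture and 0.969 to 1.000 for IGMV, with coverage 79-81%. If it carries the acupuncture identifier, the IGMV ratio is 0.992, 0.961, 0.924 (4 groups) or 0.982, 0.917, 0.848 (2 groups).

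**Does a two-effect model help at this size?** In simulation with variances estimated by REML (10,000 runs per cell, equal ICC, combined arm coded by IGMV group, acupuncture effect), the single identifier covers 0.759 to 0.793 and two group effects cover 0.791 to 0.808. At least one of the two variances is estimated at zero in 69-88% of runs.

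**The case against.** The strongest reply is that the text is ambiguous rather than shown to be wrong. A reader might infer that the model certainly drops one source of clustering in the combined arm. The documents do not support that. Group could mean a treatment group, which the wording of Section 9.1 favours, or an enrolment wave, since Section 3 says "The full enrollment period for the study will take place in waves" and Section 10.3.3 speaks of cohorts. If combined-arm participants formed their own closed groups in both formats, one identifier would be enough, although no section says they will. An analyst who keeps strict nesting could also give each group combination its own identifier, and most of the shortfall then disappears under equal ICCs and aligned cohorts. This part of the reply stands, and it is why the size is given by coding.

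It is also fair that nothing shows acupuncture clustering to be as strong as IGMV clustering. Section 5 describes individual diagnosis and needling in a shared room, whereas IGMV is built on check-in and peer support. With IGMV-only clustering and the IGMV identifier, the error is negligible. Finally, Section 9.2 calls these analyses exploratory, and two group effects raise simulated coverage by only about 1 to 3 points.

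What remains is that no single identifier lets the model separate the two kinds of clustering for the combined arm, and the choice among codings is left open. The wave reading does not help, because it separates neither.

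**Conclusion.** The point holds in a limited form. As written, the model cannot represent both sources of clustering separately for a quarter of the sample, and it cannot estimate the two within-group correlations.

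On the assumptions above (8 completers per arm, 2 to 4 groups per format, equal ICC 0.01 to 0.10):
- One format's identifier for the combined arm: the other intervention's SE is about 1-13% too small, and the one-sided 80% limit covers about 77-80%.
- An identifier per group combination: both SEs are at most about 4% too small if cohorts stay together (coverage 79-80%), and up to about 7% if memberships cross.
- Wave: both SEs are about 1-15% too small (coverage 76-80%).

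The upper ends need ICC 0.10 and only two groups; at ICC 0.01 no coding gives more than about 2%.

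Two stronger inferences are not supported. A reader might think the decision to proceed is compromised, but Section 9.1 turns on the sign of the estimate ("If the estimated effect size from the pilot is larger than zero") together with feasibility and acceptability, not on its SE. The primary feasibility outcome, the percentage of confirmed eligible patients randomized, does not use this model. A reader might also project the undercoverage onto the main trial. Section 9.2 promises only a similar analysis and uses the pilot to refine the plan, so the main trial's final model is not settled here.

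**What to change.** In Section 9.2, replace the nested group term with separate random effects for acupuncture group and for IGMV group, each zero for non-members. Combined-arm participants then carry both and waitlist participants neither. Define each kind of group (for example, by starting cohort) and record both memberships for every participant.

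With 40 people a group variance will often be estimated at zero, so state in advance how this will be reported. One option is the REML result beside the standard errors recomputed at assumed ICCs of 0.01, 0.05 and 0.10.

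The cost is a change of SAP wording and two recorded identifiers, with no new outcome data. The downside is the unstable variance estimates, which the sensitivity analysis makes visible but does not remove.
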